#### 6.1.8.3. Causality/Drug Relationship Assessment

The relationship of the event to the study drug should be determined by the investigator according to the following criteria:

- **Definitely related:** The event follows a reasonable temporal sequence from the time of drug administration that cannot be explained, follows a known or expected response pattern to the study drug, that is confirmed by improvement on stopping and reappearance of the event on repeated exposure and that could not be reasonably explained by other factors such as the patient's clinical condition, intercurrent illness, or concomitant drugs.
- **Not related:** The event is most likely produced by other factors such as the patient's clinical condition, intercurrent illness, or concomitant drugs, and does not follow a

known response pattern to the study drug, or the temporal relationship of the event to study drug administration makes a causal relationship unlikely.

- Possibly related: The event follows a reasonable temporal sequence from the time of drug administration, and/or follows a known response pattern to the study drug, but could have been produced by other factors such as the patient's clinical condition, intercurrent illness, or concomitant drugs.
- Unlikely related: The event follows little or no temporal sequence from the time of drug administration that makes a causal relationship improbable and/or other factors such as the patient's clinical condition, intercurrent illness, or concomitant drugs is a more likely alternative.
- Probably related: The event follows a reasonable temporal sequence from the time of drug administration, and/or follows a known response pattern to the study drug, and cannot be reasonably explained by other factors such as the patient's clinical condition, intercurrent illness, or concomitant drugs.

#### 6.1.8.4. Definition of Serious Adverse Events

A serious AE (SAE) is any AE that fulfills any of the following criteria, as per 21 CFR 312.32:

- Results in death;
- Is life-threatening;
- Requires in-patient hospitalization or prolongation of existing hospitalization;
- Results in persistent or significant disability or incapacity;
- Is a congenital anomaly or birth defect;
- Is medically significant or requires intervention to prevent one of the outcomes listed above.

Serious AEs will be captured from the time of consent through the end of the study.

#### 6.1.8.5. Serious Adverse Events Actions Taken

Actions taken may consist of:

- None: No action taken
- Treatment: Standard of care measures instituted
- Drug withdrawn: Study medication was permanently discontinued because of the AE
- Unknown: Not known, not observed, not recorded, or refused

#### 6.1.8.6. Serious Adverse Events Outcome at the Time of Last Observation

The outcome at the time of last observation will be classified as:

- Recovered/resolved
- Recovered/resolved with sequelae

- Not recovered/not resolved
- Death
- Unknown

#### **6.1.8.7. Adverse Event Recording and Reporting**

Adverse events will be recorded throughout the study in the source documents and in the CRFs. The investigator will rate AEs for seriousness, intensity, causality, action taken, and outcome as described in the previous section.

Expedited reporting is required for serious unexpected adverse drug reactions. Fatal or life-threatening unexpected drug reactions must be reported by the Sponsor to regulatory agencies no more than 7 days after the Sponsor's first knowledge of the reaction; followed by as complete a report as possible within 8 additional days. Unexpected drug reactions must be reported no later than 15 days after the Sponsor's first knowledge of the reaction. In order to comply with these requirements, the investigator or delegate must inform the Sponsor immediately upon occurrence of any SAE. The site will complete the SAE Report Form as thoroughly as possible and e-mail it to Insys within 24 hours of the investigators first knowledge of the event.

Sponsor contact information is listed below:

**Insys Development Company, Inc.**

Email: [[contact]](mailto:[contact])

These SAE reports must contain the following information:

- A. Study name/number
- B. Study drug
- C. Investigator details (name, phone, fax, e-mail)
- D. Patient number
- E. Patient initials
- F. Patient demographics
- G. Clinical event
  - 1) Description
  - 2) Date of onset
  - 3) Treatment (drug, dose, dosage form)
  - 4) Adverse event relationship to study drug
  - 5) Action taken regarding study drug in direct relationship to the AE
- H. If the AE was fatal or life-threatening
- I. Cause of death (whether or not the death was related to study drug)

J. Autopsy findings (if available)

The Sponsor or its representative will be responsible for notification to regulatory agencies.

**6.1.8.8. Adverse Event Follow-Up**

All non-serious AEs that are not related or unlikely to be related to study treatment will be followed until the end of study participation. All SAEs or AEs that are considered as possibly, probably, or definitely related to treatment will be followed until resolution or stabilization.

**6.1.8.9. Special Considerations**

Cannabidiol inhibits drug metabolism mediated by a subset of CYP proteins (see Section Section 1.1.2). Thus, the investigator and study center staff should monitor patients who are taking concomitant medications that are metabolized by CYP2C19, CYP2C9, CYP2D6, CYP3A4, CYP1A2, or by P-glycoprotein with special care..

## 7. STUDY PROCEDURES

Prior to performing any study related procedures or assessments, the Investigator will ensure that the patients and/or their parent(s)/caregiver(s) (if applicable) provide written informed consent and that the pediatric patient provides assent (as appropriate). Patients and their parent(s)/caregiver(s) (if applicable) will receive a copy of the informed consent form (ICF) and assent form for review and must provide fully informed consent prior to study participation.

The consent process must be conducted and the ICF signed before any study procedures. See Section 11.4 for guidelines regarding patient consent and assent.

The assessments and procedures that will be conducted during this study are summarized in [Table 1](#).

### 7.1. Safety Period

#### 7.1.1. Visit 1 (Day 1)

The following procedures and assessments will be performed:

- Review/Assess past/current AEDs and concomitant medications.
- Record vital signs, collect blood samples for clinical labs, and collect urine sample for urinalysis.
- Urine dipstick pregnancy test (all female patients of childbearing potential).
- Perform physical and brief neurological examinations.
- 12-lead ECG.
- Collect/review/dispense CBD (dose may be modified up to 40 mg/kg/day at investigator's discretion).
- Perform drug accountability.
- Review AEs.

#### 7.1.2. Monthly (Visits 2, 3, and 4) and Quarterly (Visits 5 and 6) Visits

The following procedures and assessments will be performed:

- Review/Assess past/current AEDs and concomitant medications.
- Record vital signs, collect blood samples for clinical labs, complete 12-lead ECG, and collect urine sample for urinalysis.
- Perform physical and brief neurological examinations.
- Collect/review/dispense CBD (dose may be modified up to 40 mg/kg/day at investigator's discretion).
- Perform drug accountability.
- Review AEs.

## 7.2. End of Study (Visit 7) or Early Withdrawal

The following procedures and assessments will be performed:

- Review/assess past/current AEDs and concomitant medications.
- Record vital signs, collect blood samples for clinical labs, complete 12-lead ECG, and collect urine sample for urinalysis.
- Perform physical and brief neurological examinations.
- Collect/review CBD (dose may be modified up to 40 mg/kg/day at investigator's discretion).
- Perform drug accountability.
- Review AEs.
- Complete C-SSRS.
- Urine dipstick pregnancy test (all female patients of childbearing potential).
- Dispense CBD for Taper Period.
- End of Study assessments (If the patient withdraws prematurely from the Safety Period, all Visit 7 (End of Study) procedures should be conducted. Site staff will follow-up with the patient 4 weeks after completion of treatment via the telephone to collect information regarding AEs, AEDs, and concomitant medications.

## 7.3. Taper Period (Visit 8)

The following procedures and assessments will be performed:

- Collect CBD.
- Review AEs.

## 7.4. Follow-Up Period (Visit 9)

The following assessments will be performed by phone call 30 days after Visit 7 (End of Study) the last study dose:

- Review/assess past/current AEDs and concomitant medications.
- Review AEs.

## 8. STATISTICS

### 8.1. Safety Endpoints

Changes in safety endpoints will be reported as mean/median change from baseline at relevant time points and as a listing of events that fall outside normal limits. Baseline is defined as Visit 6 of INS011-17-103.

- Incidence, type, and severity of AEs and serious adverse events (SAEs) associated with Cannabidiol Oral Solution (i.e., treatment-emergent adverse events [TEAEs]).
- Changes from baseline in vital signs, physical exam (including height and weight), ECG findings, and laboratory values (hematology, chemistry, and urinalysis).
- Changes from baseline in neurological exam.

### 8.2. Sample Size Determination

The sample size is based on successful completion of INS011-17-103, with a maximum of 30 patients.

### 8.3. Analysis Populations

Statistical analysis will be conducted on all enrolled patients.

### 8.4. Statistical Analyses

This section presents a summary of the planned statistical analyses. A Statistical Analysis Plan (SAP) that describes the details of the analyses to be conducted will be finalized prior to database lock.

Summary statistics will be provided for the variables described as follows. For continuous variables, these statistics will typically include the number of patients, mean, standard deviation, median, minimum, and maximum. For categorical variables, these statistics will typically include the number and percentage of patients in each category.

#### 8.4.1. Study Patients and Demographics

##### 8.4.1.1. Disposition and Withdrawals

The numbers of patients entering, completing, and withdrawing, along with reasons for withdrawal, will be tabulated overall and by modal dose group. For each patient, the modal dose is the dose with the longest exposure during the study.

##### 8.4.1.2. Protocol Deviations

Protocol deviations will be identified and classified as minor or major and listed.

##### 8.4.1.3. Demographics and Other Baseline Characteristics

Demographic and baseline characteristics (including age, gender, race, weight, height, and BMI) will be summarized by for the overall population by descriptive statistics. No formal statistical

analyses will be performed. Medical history, clinical laboratory test results, and ECG assessments will be listed and summarized by descriptive statistics.

Prior and concomitant medications will be summarized by the number and percentage of patients taking each medication. They will also be classified by using the World Health Organization Drug Dictionary Anatomical Therapeutic Chemical classes and preferred terms.

#### **8.4.2. Exposure and Compliance**

The exposure to study medication will be summarized by descriptive statistics. Any compliance deviations will be listed.

#### **8.4.3. Safety and Tolerability Analyses**

No formal inferential analyses will be conducted for safety variables. Data listings will be provided for protocol-specified safety data.

##### **8.4.3.1. Adverse Events**

The Medical Dictionary for Regulatory Activities (MedDRA, version 20.0 or higher) will be used to classify all AEs. Adverse event summaries will include only TEAEs, which will be summarized for each modal dose group. For each patient, the modal dose is the dose with the longest exposure during the study.

The number and percentage of patients with AEs will be displayed for each treatment group by system organ class and preferred term. Summaries of AEs by severity and relationship to the IP will also be provided. Serious AEs (SAEs) and AEs resulting in discontinuation will be summarized separately in a similar manner. Patient listings of AEs and SAEs will be produced.

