In addition, a long-term safety study (Protocol INS011-14-030) for subjects enrolled in the PK study above was recently completed. Fifty-two of 61 subjects from INS011-14-029 enrolled; 45 subjects completed the study. There were seven early termination subjects (two for withdrawal of consent, two for AEs of aggressions and sleepiness/irritability, one for the SAE of worsening seizures, one for lack of efficacy, and one subject with a genetic mutation died from systemic sepsis and multi-organ failure considered nonrelated). Overall, 91% of the subjects were taking doses greater than 20 mg/kg/day, with 38% of subjects tolerating 40 mg/kg/day. The most common drug-related AEs reported were anemia (5 subjects), somnolence (4 subjects), and weight increased (4 subjects). However, the weight increases ranged from a little over 2 lbs to approximately 7 lbs.

During the study, trough PK values were drawn and interim PK data for CBD and 7-OH CBD from Visit 5 (Week 4) to Visit 8 (Week 24) were analyzed. Dose-normalized mean trough CBD concentrations ranged from 11.9 to 16 (ng/mL)/(mg/kg), showing relatively stable levels for up to 6 months dosing Cannabidiol Oral Solution at various dose levels. After one month of dosing, there did not appear to be much accumulation, even though early accumulation had likely happened when compared with INS011-14-029 results. High variability in trough CBD concentrations was observed, but the extent of variability between visits was similar as reported in the previous 029 study.

An open-label study of Cannabidiol Oral Solution (20 mg/kg/day and 40 mg/kg/day) in pediatric subjects with infantile spasms refractory to ACTH and vigabatrin recently was halted due to futility (Protocol INS011-15-054) because only one out of nine patients achieved a complete response.

A food effect study of Cannabidiol Oral Solution in normal healthy adults (Protocol INS011-15-043) recently completed and the results are presented in the IB. Analysis demonstrated significantly higher CBD levels when administered with food.

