### 3. INVESTIGATIONAL PLAN

#### 3.1. Overall Study Design

This is a multicenter, open-label, flexible dose study designed to assess the long-term safety and tolerability of CBD in doses ranging from 20 mg/kg/day to 40 mg/kg/day in patients with treatment-resistant childhood absence seizures. Patients must have completed INS011-17-103 to be eligible.

The Investigator will ensure that the patients legal representative [parent(s)/caregiver(s)] will receive a copy of the informed consent form for review and provide full informed consent prior to study participation.

Patients should enroll in Long-Term Safety Study (INS011-17-113) after completing Study INS011-17-103 Visit 6 (End of Study) to avoid interruption of the investigational product. Patients will have up to 2 weeks to enroll in INS011-17-113. The first visit (Visit 1) for INS011-17-113 will be after the completion of Visit 6 of INS011-17-103.

Patients will continue to receive CBD treatment for approximately 48 weeks. Patients will remain on their assigned dose or may be titrated up to a higher dose level if the Data Monitoring Committee has approved the higher dose level in INS011-17-103. **If any participant does not enroll within the 2 week window, the patient will not be eligible to enroll into the study.**

The study will consist of a Safety Period (48±2 weeks), Taper Period (10±3 days), and a Follow-up Period (30±5 days). Treatment visits will be scheduled monthly for the first 3 months and then quarterly over the remaining 9 months. All patients will complete a Visit 7 (End of Study) or Early Withdrawal Visit regardless of when they stop treatment/complete the study. A Follow-Up telephone call (Visit 9) will occur 30 days after the end of either the End of Study (Visit 7) or Early Withdrawal.

In this study, all patients will be dosed as follows:

- Once the informed consent for INS011-17-113 is provided within the required time frame, initially the patient will receive the same dose as was administered during INS011-17-103. If tolerability issues occurred during INS011-17-103, the dose can be decreased if the dose was greater than 20 mg/kg/day. If the patient received 20 mg/kg/day and the physician wants to decrease the dose, the patient should be discontinued.

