#### 3.2.2. Exclusion Criteria

Patients will be excluded for any of the following:

1. Patient or parent(s)/caregiver(s) have daily commitments during the study duration that would interfere with attending all study visits.
2. Experienced an anoxic episode related to study drug requiring resuscitation during their previous study.

3. Developed an adverse event thought to be related to CBD in the previous study and for whom the Investigator determines that continuing treatment with CBD would not be in the best interest of the patient.
4. Evidence of other clinically significant disease such as unstable hepatic, hematological, renal, cardiovascular, gastrointestinal, immunological, or pulmonary diseases or ongoing malignancies.
5. Compromised respiratory function or severe respiratory insufficiency.
6. Clinically significant abnormal laboratory values within the past 14 days, including:
  - a. Liver function tests (LFTs) such as albumin, direct bilirubin, total bilirubin, aspartate aminotransferase (AST), and alanine aminotransferase (ALT)  $\geq$  3 times the upper limit of normal (ULN).
7. In the opinion of the investigator, the patient is unsuitable in any other way to participate in this study.

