### **3.4. Dose Adjustment Criteria**

Doses of CBD may be adjusted at the investigator's discretion up to a maximum of 40 mg/kg/day only if the Data Monitoring Committee has approved the higher dose level in INS011-17-103. Doses greater than 40 mg/kg/day are not allowed. All dose changes must be clearly documented in the eCRF.

Antiepileptic drugs (AEDs) or therapies (e.g., VNS and ketogenic diet) may be initiated, discontinued or dose adjusted as needed. Any changes must be documented in the eCRF.

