#### 6.1.8.2. Classification of Adverse Events

Adverse events are to be recorded on the AE page of the patient's case report form (CRF). Severity will be graded according to the following definitions:

- **Mild:** The patient experiences awareness of symptoms but these are easily tolerated or managed without specific treatment.
- **Moderate:** The patient experiences discomfort enough to cause interference with usual activity, and/or the condition requires specific treatment.
- **Severe:** The patient is incapacitated with inability to work or do usual activity, and/or the event requires significant treatment measures.

Action taken will be categorized as none, study drug discontinued, dose modified, required concomitant medication, required procedure, or other.

Event outcome at resolution or time of last follow-up will recorded as event resolved, resolved with sequelae, ongoing, or death.

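### Section 8.4.3.1 tabulates all of a patient's AEs under the longest-exposure dose, so an AE followed by an early step-down, or arising after a late increase, is shown under a lower dose than the one at onset (minor, descriptive)

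*Combined protocol and SAP*

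**What the plan says.** Section 8.4.3.1 states that TEAEs are "summarized for each modal dose group. For each patient, the modal dose is the dose with the longest exposure during the study". It goes on: "Serious AEs (SAEs) and AEs resulting in discontinuation will be summarized separately in a similar manner". Each patient therefore sits in one dose column with all of his or her events. Section 8.4.1.1 uses the same definition for disposition.

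The dose is not fixed. Section 3.4 says "Doses of CBD may be adjusted at the investigator's discretion up to a maximum of 40 mg/kg/day", provided the parent study's Data Monitoring Committee has approved the higher level. Section 7.1.2 repeats at each monthly and quarterly visit that the "dose may be modified up to 40 mg/kg/day at investigator's discretion". Section 6.1.8.2 makes a dose change one of the coded responses to an AE: "Action taken will be categorized as none, study drug discontinued, dose modified". It states no direction for the change.

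Section 8.4.3.1 also plans patient listings of AEs and SAEs without naming their columns. No section supplied plans a summary by dose at onset. Section 8.4 describes itself as a summary and leaves detail to a SAP whose text is not among the documents.

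**The concern.** The classifying variable is determined partly by the outcome it is used to describe. A patient who has an AE at 40 mg/kg/day and steps down early moves to a lower column and takes the event along. The higher-dose column keeps those who had no event or whose event led to no reduction. A late increase has the same effect by another route, because events at the new dose stay with the longer, earlier one. An early increase in a patient who already had an AE pushes the other way.

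What is at stake is the reading of tolerability by dose. Section 1.3 reports AEs that rose with dose in the sponsor's earlier fixed-cohort study, somnolence and diarrhea among them, and Section 6.1.8.1 names both as AEs of special interest. A by-dose table that flattens or reverses such a gradient could be read as evidence against one.

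**Working it through.** **Inputs from the documents.** 48 weeks of dosing (Section 3.1), which is 336 days; visits at weeks 4, 8, 12, 24, 36 and 48 (Table 1); doses of 20 to 40 mg/kg/day (Section 3.1); at most 30 patients (Section 8.2). The plan states no figure to reproduce.

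**Step 1: when the column changes.** With two dose levels, the lower one is modal if the step-down comes before day 336/2 = 168 (week 24). One increase at week 36 leaves 36 weeks at the lower dose and 48 − 36 = 12 at the higher, so the lower dose is modal.

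**Step 2: how many AEs fall early enough.** With a constant weekly hazard h, the share of first AEs that occur before week 24, among patients with one by week 48, is (1 − e^(−24h)) / (1 − e^(−48h)). This is 0.50 as h approaches 0, and 0.53, 0.56 and 0.62 at h = 0.005, 0.01 and 0.02.

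**Step 3: a hand example (assumed counts).** Ten patients start at 40 and five have a given AE; ten start at 30 and two have it. Three of the five step down early to 30.

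| Table | 40 mg/kg/day | 30 mg/kg/day |
|---|---|---|
| Modal dose | 2/7 = 29% | 5/13 = 38% |
| Dose at onset, patients ever exposed | 5/10 = 50% | 2/13 = 15% |

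**Step 4: simulation (assumed rates).** The documents give neither step-down rates nor AE rates by dose. Assumptions: 336 days, equal numbers starting at each dose, each AE at 30 or 40 leads to a one-level step-down with the stated probability, ties go to the higher dose, taper excluded, no dropout, no up-titration. Hazards are per 100 patient-weeks at 20/30/40.

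| Hazards | Quantity | No step-down | 10% | 25% | 50% |
|---|---|---|---|---|---|
| 0.5/1/2 | 40:20 incidence ratio | 2.9 | 2.6 | 2.2 | 1.7 |
| 1/1.1/1.2 | Incidence % at 20/30/40 | 38/41/44 | 40/41/42 | 42/41/40 | 45/41/35 |
| 1/1/1 | Incidence % at 20/30/40 | 38/38/38 | 39/38/36 | 42/38/34 | 45/38/30 |

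The column without step-down is 1 − e^(−48h): for example 1 − e^(−0.96) = 0.617 at 40 and 1 − e^(−0.24) = 0.213 at 20, a ratio of 2.9. In the first row the ratio reaches 1.3 and 1.0 at 75 and 100% step-down.

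**Step 5: up-titration, hazards 0.5/1/2.** If only patients with a prior AE are raised (15 to 30% per visit), the ratio is 3.4 to 3.8 with no step-down, 2.7 to 3.2 at 25% and 2.2 to 2.7 at 50%. If only AE-free patients are raised, it falls to about 2.3 and 1.8 at 15 and 30% per visit, with no step-down at all.

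**Step 6: a trial of 30, ten per starting dose, hazards 0.5/1/2.** About 10 × 0.617 = 6.2 patients have a first AE at 40. Of these, 1.1 (25% step-down) to 2.1 (50%) are tabulated lower. The chance that the AE percentage at 40 is no higher than at 20 rises from 4% to 8% and about 17%. If entry selection halves hazards in the first 12 weeks, 0.8 to 1.6 of 5.7 patients move, and the ratio goes from 3.0 to 2.3 and 1.9. With no AEs in those weeks, 0.6 to 1.1 of 5.1 move.

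**Step 7: a rare AE.** Section 1.3 says of the earlier extension study: "The most common drug-related AEs reported were anemia (5 subjects), somnolence (4 subjects), and weight increased (4 subjects"). With 52 enrolled, somnolence is 4/52 = 7.7% (exact 95% CI 2.1 to 18.5%). Taking 7.7% at 40, with half and a quarter of that hazard at 30 and 20, 0.1 to 0.2 of 0.8 patients move. The chance that the percentage at 40 is no higher than at 20 is already 52% from sampling alone; it becomes 56% and 60%.

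**Step 8: dose at onset over patient-time.** In the same simulations the 40:20 rate ratio is 3.9 to 4.1 (true 2/0.5 = 4.0), 3.7 to 3.9 if early hazards are lower, and 0.99 to 1.01 with no dose effect.

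**The case against.** Modal dose is a disclosed, prespecified convention. The objective in Section 2 is overall long-term safety and tolerability; no endpoint compares doses, Section 8.4.3 rules out inference, and no dose decision rests on this table. On that view, asking for another descriptive table is a preference. This stands as a limit on severity. But the plan does choose to show AEs by dose, and readers will read that table by dose.

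The missing SAP text may already contain such a table. That cannot be excluded; the point is confined to what was supplied. Listings are planned, dose changes and dosing dates are recorded (Sections 3.4 and 4.4), and SAE reports carry dose (Section 6.1.8.7). With 30 patients at most, someone could read the cases one by one. This softens the gap without closing it, because the listings' columns are unspecified.

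The step-down probabilities are assumed, and applying them to every AE includes events unrelated to drug. That is fair: the reversed gradients need frequent step-downs or a shallow true gradient. Entry selection also limits the effect. Patients completed the parent study, and those who "Developed an adverse event thought to be related to CBD in the previous study" can be excluded on the investigator's judgement. In addition, "If tolerability issues occurred during INS011-17-103, the dose can be decreased if the dose was greater than 20 mg/kg/day"; a decrease made at entry for that reason has no in-study AE to misplace. In-study decreases rest on the general wording of Sections 3.4 and 7.1.2, which does not restrict changes to increases.

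Last, the good performance in Step 8 is partly built in, because the simulated hazard depends only on current dose. Transaminase elevations, another AE of special interest, are found at scheduled visits up to 12 weeks apart, so dose at onset may really be dose at detection. Both points stand as cautions on the added table.

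**Conclusion.** The concern holds and is minor. The rule in Section 8.4.3.1, combined with in-study dose changes, places some AEs under a lower dose than the one being taken at onset. Early step-downs after an AE and late increases both flatten the tabulated gradient; early increases after an AE partly offset this. For common AEs the effect could be visible: under the assumed hazards the 40:20 ratio drops from 2.9 to between 2.6 and 1.7 for step-down after 10 to 50% of AEs, and one to two patients change column at 25 to 50%. For rare AEs, sampling error dominates. The direction follows from the rule; the size rests on assumed hazards, step-down rates and starting-dose split. Overall AE incidence, the sample size and any decision rule are untouched.

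**What to change.** Keep the modal-dose table. Add to Section 8.4.3.1 and the SAP a supplementary table of TEAEs, SAEs and AEs leading to discontinuation by dose at onset, with an all-patients column. Give patients ever exposed and patient-time at each dose as denominators, and state whether the rate is all events over total time or first events over time to first event. Show AEs with onset in the taper or follow-up separately, and note that laboratory AEs are dated at detection. At the least, put dose at onset in the planned AE and SAE listings.

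The cost is wording and programming, with no new visit and no change to any dosing rule. Dose changes and dosing dates are already recorded. Confirm that AE onset date is a field on the AE page, since the documents name it only for SAE reports (Section 6.1.8.7). Two downsides should be stated with the table: a patient can appear in more than one dose column, and later time at the highest dose comes from patients who tolerated it.
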